5.4.3 Other Activity Analyses

The number of subjects with partial clearance ($\geq 75\%$) of treated AK lesions at Day 57 will be analyzed in the same way as the primary activity endpoint.

5.4.4 Exploratory Analyses

Analysis visits in the Recurrence Follow-up Period will be mapped based on the actual days relative to the Day 57 visit of each subject:

Actual Visit Date - Day 57 Visit Date	Analysis Visit
Between 1 and 136 (inclusive)	3 MONTHS POST-DAY 57
Between 137 and 226 (inclusive)	6 MONTHS POST-DAY 57
Between 227 and 316 (inclusive)	9 MONTHS POST-DAY 57
317 and Beyond	12 MONTHS POST-DAY 57

Recurrence rates and the associated 95% CIs will be evaluated with a Kaplan-Meier method at each post-Day 57 analysis visit:

$$RR_j = 1 - S_j, \text{ with } S_j = S_{j-1} * [1 - R_j/N_j] \text{ for } j > 0 \text{ and } S_0 = 1$$

where

j: Visit j

RR_j: Recurrence rate at visit j

S_j: Sustained response rate at visit j

R_j: Number of subjects with AK lesion recurrence at visit j

N_j: Number of subjects at risk at visit j

Early-discontinued subjects with no AK recurrence will be considered as censored at the last visit with AK lesion assessment. Completed subjects with no AK recurrence will be considered as censored at 12 Months post-Day 57 visit. The number of subjects at risk for visit j will be calculated as $N_{j-1} - R_{j-1} - C_{j-1}$, where N_{j-1} is the number of subjects at risk at the visit j-1. R_{j-1} is the number of subjects with recurrence at the visit j-1 and C_{j-1} is the number of subjects censored at visit j-1.

The recurrence rates and their associated 95% CIs will be presented by analysis visit, treatment location, and cohort for the Recurrence Follow-up Set.

Similarly, the sustained response rate and its 95% CI at 12 Months Post-Day 57 will be estimated by treatment location and cohort for the Recurrence Follow-up Set.

A listing of subjects who is included in the Kaplan-Meier analysis will be presented to provide their event or censoring details.

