9.1.3 Follow-up Period

After the Treatment Period for both cohorts, there will be Follow-up Visits at Days 8, 15, 29, and 57 to assess safety, activity, LSRs, pigmentation, and scarring.

For subjects who do not have complete response at Day 57, Day 57 is their Final Visit.

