9.7.1.6 Activity Analyses

AK lesion counts will be summarized by cohort at Day 1 (pretreatment) and at each subsequent timepoint for subjects in the Full Analysis Set and the Per-Protocol Set.

A 95% confidence interval (CI) for the complete clearance (response rate) at Day 57 will be estimated by cohort in the Evaluable Set.

Recurrence rates for all subjects who achieved complete clearance at Day 57 will be estimated by timepoint and cohort in the Evaluable Set.

A 95% CI for the sustained response rate at 12 months post-Day 57 will be estimated by cohort in the Evaluable Set.

Both cohorts will be analyzed with the same statistical methods. Since this is not a dose regimen randomized study, any contrast between the 2 cohorts will mainly be noninferential and consist of listings, graphs, and descriptive statistics.

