3.1.2 Secondary Objectives

- To assess the activity of KX2-391 Ointment 1% during Days 1-57
- To assess the safety and tolerability of KX2-391 Ointment 1% in subjects with AK on the face or scalp
- To assess dose regimens by contrasting 5-day treatment with 3-day treatment in terms of the activity and safety of KX2-391 Ointment 1% in subjects with AK on the face or scalp

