3.1.3 Exploratory Objectives

- To determine recurrence rates up to 12 months post-Day 57 for subjects who show response at Day 57
- To determine sustained response rates at 12 months post-Day 57 for subjects who show response at Day 57

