5.2 Study Subjects

5.2.1 Definitions of Analysis Sets

- Per-Protocol Set: the group of protocol-eligible subjects who receive 5 days (Cohort 1) or 3 days (Cohort 2) of study treatment and complete at least one scheduled post-treatment AK lesion evaluation
- Evaluable Set: the group of protocol-eligible subjects who receive 5 days (Cohort 1) or 3 days (Cohort 2) of treatment and complete Day 1 and Day 57 AK lesion evaluations
- Safety Analysis/Full Analysis Set: the group of subjects who receive at least one dose of study treatment
- Recurrence Follow-up Set: the group of subjects who achieve complete clearance at Day 57

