5.3 Data Analysis General Considerations

Both cohorts will be analyzed with the same statistical methods. Since this is not a dose regimen-randomized study, contrast between the 2 cohorts may be performed, but would mainly be noninferential, and consist of listings and descriptive statistics.

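### The 12-month sustained response rate is planned only among Day 57 responders, so the side-by-side cohort figures do not show which regimen leaves more subjects clear at 12 months

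*SAP*

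**What the plan says.** SAP 5.4.4 estimates recurrence by a Kaplan-Meier recursion with S0 = 1 at Day 57. The 12-month sustained response rate, from the same method, "will be estimated by treatment location and cohort for the Recurrence Follow-up Set". SAP 5.2.1 defines that set as "the group of subjects who achieve complete clearance at Day 57". SAP 5.4.5 repeats the 12-month rate by cohort in subgroups. SAP 5.4.1 gives the Day 57 complete response rate separately, in the Evaluable Set, with an exact CI. No 12-month rate with all evaluable or all treated subjects as denominator is planned.

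Protocol 9.7.1.6 says: "A 95% CI for the sustained response rate at 12 months post-Day 57 will be estimated by cohort in the Evaluable Set". The exploratory objective (SAP 3.1.3, matching Protocol 8.3) is conditional on response: "To determine sustained response rates at 12 months post-Day 57 for subjects who show response at Day 57".

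A secondary objective (SAP 3.1.2) is "To assess dose regimens by contrasting 5-day treatment with 3-day treatment in terms of the activity and safety". SAP 5.3 qualifies this: "contrast between the 2 cohorts may be performed, but would mainly be noninferential, and consist of listings and descriptive statistics".

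SAP Section 7 declares the new Recurrence Follow-up Set and the Kaplan-Meier method. It does not comment on the protocol's reference to the Evaluable Set for sustained response.

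**The concern.** The responder set is formed after treatment and by treatment. A regimen that also clears more resistant subjects brings them into its own denominator. If those subjects relapse more often, its responder-only rate falls even though it has left more people clear. Because the curve starts at 1, the Day 57 response rate does not enter the 12-month figure at all.

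The 12-month rates will nevertheless stand side by side by cohort, in a study that has a regimen contrast on activity among its objectives. A reader who takes the higher rate as the better 12-month outcome could be misled. A rate of the order of 65% could also be taken to apply to everyone treated.

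**Working it through.** **Inputs from the documents.** Evaluable subjects per cohort: 60 (SAP Section 4). Planned Day 57 complete response: 35% (SAP Section 4). Recurrence of about 35% (Protocol 7.2); this figure is for current approved treatments, not this drug, and has no time horizon, so it is used here as an assumption. The documents state no planning figure for sustained response, so there is none to reproduce. The enrolment target is consistent with the 60: 60/(1 − 0.25) = 80.

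**Step 1: the two rates at planning values.** Write CR for the Day 57 response rate and S for 12-month sustained response among responders.
- Responders: 0.35 × 60 = 21.
- Responder-only rate: S = 1 − 0.35 = 0.65.
- All-evaluable rate, with non-responders as failures: CR × S = 0.35 × 0.65 = 0.2275, about 23%.
- Exact 95% CIs at the nearby whole number, without censoring: 14/21 gives 43% to 85%; 14/60 gives 13% to 36%.

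No 12-month data on non-responders are needed. The protocol ends their follow-up (9.1.3: "For subjects who do not have complete response at Day 57, Day 57 is their Final Visit"), but by definition they cannot be sustained responders.

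**Step 2: when the two rates disagree.** Cohort 2 has the higher responder-only rate but the lower all-evaluable rate when S2 > S1 and CR2 × S2 < CR1 × S1. With CR1 = 0.35 and S1 = 0.65, that is 0.65 < S2 < 0.2275/CR2. CR2 is not in the documents, so a range is assumed:
- CR2 = 0.30: S2 between 0.65 and 0.76.
- CR2 = 0.25: S2 between 0.65 and 0.91.
- CR2 = 0.20: the bound is 0.2275/0.20 = 1.14, so any S2 above 0.65.

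**Step 3: selection alone can produce this.** Assume 30 easy and 30 hard subjects per cohort, and 12-month durability after clearance of 70% (easy) and 40% (hard) under both regimens. Assume Day 57 clearance of 60% and 40% (5-day) and of 50% and 15% (3-day).

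| | 5-day | 3-day |
|---|---|---|
| Cleared at Day 57 | 18 + 12 = 30 | 15 + 4.5 = 19.5 |
| Clear at 12 months | 12.6 + 4.8 = 17.4 | 10.5 + 1.8 = 12.3 |
| Responder-only rate | 17.4/30 = 58% | 12.3/19.5 = 63% |
| All-evaluable rate | 17.4/60 = 29% | 12.3/60 = 20.5% |

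Durability within each stratum is identical, so the 3-day regimen's higher responder-only rate comes only from who was cleared.

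**Step 4: how often observed rankings would differ.** In simulated trials with 60 per cohort and no censoring, the two observed rankings were opposite in about 33% of trials (CR 0.35 and 0.25, S 0.65 in both), 40% (same CR, S 0.60 and 0.70) and 44% (same CR, S 0.65 and 0.75). With identical true rates in both cohorts it was still 22%, so part of this is chance.

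**Step 5: variance of the added rate.** Take 60 evaluable, 39 non-responders and 14 of 21 responders sustained. The Greenwood terms are 39/(60 × 21) = 0.0310 for Day 57 and 7/(21 × 14) = 0.0238 afterwards. The standard error is (14/60) × √(0.0310 + 0.0238) = 0.055, which equals the binomial value √(0.2333 × 0.7667/60). Leaving out the Day 57 term gives (14/60) × √0.0238 = 0.036, which is too small.

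**The case against.** Several objections stand.

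- **The responder-only rate is the right answer to the exploratory objective.** Both documents word that objective as conditional on Day 57 response, and SAP 5.1.3 labels the rate accordingly.
- **A reader might infer that the SAP quietly replaced an Evaluable Set denominator.** The documents do not establish this. The preceding sentence of Protocol 9.7.1.6 places recurrence among Day 57 responders in the Evaluable Set too, so there the phrase names the population from which responders are drawn. The endpoint wording in Protocol 9.7.1.1.3 is parallel for the two rates, and Protocol 8.3 is conditional. The denominator is open.
- **A reader might infer that the plan will rank the regimens the wrong way round on durability.** It plans no ranking and no test. The 12-month rates are exploratory, the secondary activity endpoint stops at Day 57, and no passage assigns the 12-month rate to the regimen contrast. The reversal in Step 3 rests on assumed strata, and 58% against 63% on 30 and 19.5 responders is well inside sampling error.
- **The added rate is not a pure durability measure.** In Step 3 its whole difference comes from Day 57 clearance, already the primary analysis. When the responders are the evaluable ones it equals the Day 57 rate times the responder-only rate, and both are planned.

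What remains is that the product has no planned estimate or CI, and that a descriptive display can still mislead.

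**Conclusion.** The point holds as a low-cost improvement, not as an error in the exploratory analysis. Responder-only rates by cohort are a legitimate description of durability after clearance within each cohort. They are not a fair description of which regimen leaves more subjects clear at 12 months, because each regimen selects its own denominator.

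The gap between the two figures is large at planning values: 65% against about 23%, given 35% response and an assumed 35% recurrence. Opposite directions are possible over a wide range of assumed Cohort 2 values, but this is an illustration and not a prediction.

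Neither rate supports a causal comparison. The cohorts are sequential and not randomized, and the all-evaluable rate removes only the responder selection.

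**What to change.** 1. Keep the responder-only estimate in SAP 5.4.4 for the exploratory objective.
2. Add, by cohort, the 12-month sustained clearance rate in the Evaluable Set with a 95% CI. In the SAP's recursion, set N0 to the number of Evaluable subjects and R0 to the Day 57 non-responders among them, so that S0 = 1 − R0/N0. The existing at-risk and censoring rules then apply.
3. After Day 57, follow only responders who are in the Evaluable Set. SAP 5.2.1 does not require protocol eligibility or full dosing for the Recurrence Follow-up Set, so using that set unchanged would mix populations.
4. Carry the Day 57 step into the variance.
5. State that any 12-month reading between regimens uses this rate, descriptively.
6. In Section 7, clarify which denominator the protocol's Evaluable Set reference meant, and that the SAP's main sustained response rate is conditional on Day 57 response. Do not state that the base was replaced.

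The cost is a few lines of SAP text and one extra estimate per cohort, from data already collected. The downside is a lower 12-month figure beside the responder-only one. Confounding between the sequential cohorts remains.

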5.4.5 Subgroup Analysis

Complete clearance rate at Day 57, partial clearance rate at Day 57, sustained response rate at 12 Months Post-Day 57 will be analyzed by cohort in the following subgroups: age (<65, ≥65), sex (female, male), baseline AK lesion count (4, 5, 6, 7 and 8), baseline weight (< 200 and ≥200 lbs), skin type group (each skin type), study site (each study site).

5.5 Safety Analyses

All safety variables will be analyzed in the Safety/Full Analysis Set.

5.5.1 Adverse Events

All AEs, regardless of relationship to study treatment, will be collected from the time the subject signs the informed consent form through the final contact in the Follow-up Period at Day 57. In addition, treatment-related AEs/SAEs may be followed after the Day 57 visit to resolution, or if resolution is unlikely, to stabilization. For subjects participating in the Recurrence Follow-up Period, all spontaneously reported AEs will be collected whether they occurred at the treatment area or not.

For AEs, verbatim terms on the eCRF will be mapped to system organ classes (SOCs) and preferred terms (PTs) using the Medical Dictionary for Regulatory Activities (MedDRA) version 18.1.

Treatment-emergent AEs (TEAEs) will be identified, and are defined as:

- Either those AEs with an onset on or after the first dose date/time of study treatment
- Those pre-existing AEs that worsen after the first dose date/time of study treatment

If an AE cannot be determined to be treatment-emergent according to the definition above due to partial or missing dates, it will be considered as a TEAE unless it is confirmed to have stopped before the first dose date/time of study treatment.

Furthermore, to identify TEAEs that start before the Recurrence Follow-up Period, AE start dates will be determined relative to the actual Day 57 visit date for the corresponding subject. In such cases, if an AE start date cannot be confirmed to fall within the Recurrence Follow-up Period due to partial or missing dates, that AE will be considered to have started before that period.

An overall summary table of AEs will include the number of subjects with the following events for each cohort.

- Any AEs
- Any TEAEs
- Any AEs that are at least possibly related to study treatment, including those definitely related, probably related and possibly related or those with missing relationship
- Any serious AEs
- Any severe AEs
- Any AEs leading to study discontinuation
- Any AEs that are associated with death

In addition, summaries of the number of subjects with the following AEs will be displayed for each cohort:

- All TEAEs by SOC and PT
- All TEAEs by PT
- All TEAEs by PT and maximum severity (mild, moderate, or severe)
- All AEs that are at least possibly related to study treatment by SOC and PT
- All AEs that are at least possibly related to study treatment by PT
- All AEs that are at least possibly related to study treatment by PT and maximum severity (mild, moderate or severe)

Severe or serious AEs, whether treatment-emergent or not, will be presented in listings. AEs leading to treatment discontinuation will also be listed.

AEs that are collected during the Recurrence Follow-up Period (i.e. those with start dates after Day 57 visit) will be summarized and listed in the same way, but separately, for the Recurrence Follow-up Set.

Moreover, all AEs will be reviewed manually by the study Medical Monitor to identify any skin cancer-related records. Those event records will be displayed in a separate listing.

All AEs collected during the entire study including the Recurrence Follow-up Period will be presented in a subject data listing.

5.5.2 Local Skin Reactions

LSRs will be assessed using a 5-point grading scale ranging from 0 (Not Present) to 4 (Worst) for such signs as Erythema, Flaking/Scaling, Crusting, Swelling, Vesiculation/Pustulation, Erosion/Ulceration on the treatment area at the following visits: Day 1, Day 2, Day 3, Day 4 (Cohort 1 only), Day 5 (Cohort 1 only), Day 8, Day 15, Day 29, and Day 57. In addition, LSRs may be followed after the Day 57 visit to resolution, or if resolution is unlikely, to stabilization.

LSR baseline grades are defined as the LSR grades recorded at Day 1 (either pre-dose or post-dose).

The incidence of LSRs will be summarized by grade and cohort at each visit for each sign. In addition, LSR grades will be regarded as continuous values and will be summarized using descriptive statistics by cohort at each visit for each sign. Similarly, grades for each LSR sign will be visually presented in bar graphs by cohort at each visit.

Further, the incidence of the worst post-baseline LSR grade will be summarized by LSR grade and cohort for each sign.

The number of subjects with shift from baseline to the worst post-baseline grade and to the Day 57 grade will be summarized by cohort for each sign.

Furthermore, a composite LSR score will be constructed by summing the individual LSR grades for each sign at each visit. This composite score and change from baseline will be summarized by cohort at each visit using descriptive statistics. In addition, this score will be presented graphically by cohort in a line plot.

All LSR grades, including the derived composite score, and any associated comments will be displayed in data listings.

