- a For Day 57 complete responders only.
- b For subjects who do not have complete response at Day 57, Day 57 is the Final Visit.
- c For subjects who have complete response at Day 57 and no recurrence, 12 months post-Day 57 is the Final Visit. Those subjects who have AK recurrence in the treatment area will have their Final Visit at the visit when the AK recurrence is identified.
- d Assessment performed before study medication application. Day 1 evaluation will serve as baseline for these assessments.
- e Vital signs measurements will be taken after the subject has been seated for at least 5 minutes.
- f A complete PE will include weight and an assessment of HEENT, integumentary, gastrointestinal, cardiovascular, respiratory, musculoskeletal, and neurological systems. Height will be measured at Screening only.
- g Subjects must be in the recumbent position for a period of 5 minutes prior to the ECG.
- h Except for those diagnosed as having diabetes, subjects must be fasted for laboratory assessments.
- i For females of childbearing potential; urine pregnancy test on Day 1 before study medication application. All other pregnancy tests are performed with serum.
- j PK assessments on Day 1 and Day 5 at 0 hour (just before study medication application) and at 0.5 (± 5 min), 1 and 4 hours (± 10 min) after study drug application.
- k Before LSR assessment, subjects will be queried for spontaneously reported AEs.
- l Only AEs in the selected treatment area will be recorded.

Table 2 Schedule of Procedures/Assessments in Study KX01-AK-002 (Cohort 2)

Period	Screening	Treatment						Follow-up				Recurrence Follow-up ^a
		2	3	4	5 ^b	6 ^b	7	8	9	10 ^c / Early Term		
Visit	1	2	3	4	5 ^b	6 ^b	7	8	9	10 ^c / Early Term	11, 12, 13, 14 ^a	
Day	-28 to -1	1	2	3	4	5	8	15	29	57 ^c	3, 6, 9, 12 Months Post-Day 57 ^d	
Visit time window (days)	None	None	None	None			±2	±2	±2	±2	±14	
Informed consent	X											
Inclusion & exclusion criteria	X	X ^e										
Demographics	X											
Medical/surgical history	X											
AK history/AK treatment history	X											
Fitzpatrick skin-type scale	X											
Vital signs ^f	X			X			X	X	X	X		
Prior and concomitant medications/therapies	X	X ^e	X	X			X	X	X	X	X	
Physical examination, including weight and height ^g	X									X		
Treatment area identification	X	X ^e										
AK lesion count	X	X ^e					X	X	X	X	X	
ECG ^h	X	X ^h		X ^h			X			X		
Clinical chemistry, hematology, and urinalysis ⁱ	X						X			X		

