9.4.2.4 Administration of Investigational Products

The study medication is for external topical use on the treatment area. An investigational center staff member will perform the study medication applications. The staff member must wash her/his hands before and after each study medication application.

50 mg of KX2-391 Ointment 1% will be applied topically to a 25 cm² treatment area. This amount contains a total of 0.5 mg KX2-391 free base. KX2-391 Ointment 1% will be applied once daily for 5 consecutive days (Cohort 1) or 3 consecutive days (Cohort 2) (see [Table 3](#)).

The staff member will weigh the appropriate amount of study medication into a weighing boat (or equivalent) using a calibrated scale. The amount of study medication applied will be calculated by determining the difference of the weight of the weighing boat with study medication before and after application. The amount of study medication weighed will be as close to the intended dose as possible.

A study staff member will perform and document a scale accuracy check at least every day before weighing study medication.

KX2-391 Ointment 1% will be applied to the subject's treatment area using a fingertip protected with a powder-free finger cot or examination glove. The study medication will be gently and evenly rubbed over the treatment area, including its borders, until no visible accumulation is evident. The time when the study medication application is completed (Application Completion Time) will be recorded.

The study medication should remain on the treatment area. Subjects must avoid touching or wetting the treatment area for at least 12 hours from time of last application and are not allowed to apply any topical products to the treatment area (see [Section 9.4.7.3](#)). Instructions will be sent home with the subject clarifying on how to care for the treatment area.

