9.5.1.5.8 OTHER ASSESSMENTS

Concomitant Medications

Concomitant medications will be assessed at all clinic visits (Table 1 and Table 2). Any medication (including nonprescription medications) or therapy administered to the subject during the course of the study (starting at the date of informed consent) will be recorded on the Concomitant Medication CRF/eCRF. The Investigator will record any AE on the Adverse Events CRF/eCRF for which the concomitant medication/therapy was administered.

Use of sunblock or any topical products in the treatment area allowed by the Investigator will be recorded in the Concomitant Medication CRF/eCRF.

Local Skin Reactions

At every post-Screening clinic visit through Day 57 (Visit 10), the Investigator or trained designee will assess any LSR on the treatment area for signs:

- Before study medication application (on dosing days)
- After the assessment of adverse events

The LSR assessment is the Investigator's (or trained designee's) assessment of the following signs on the treatment area: erythema, flaking/scaling, crusting, swelling,

vesiculation/pustulation, and erosion/ulceration. These signs will be assessed using a grading scale ranging from 0 (not present) to 4 (worst) (Table 6).

Table 6 Local Skin Reaction Grading Criteria

Grading Criteria					
Local Skin Response	0	1	2	3	4
Erythema	Not present	Slightly pink <50%	Pink or light red >50%	Red, restricted to treatment area	Red extending outside treatment area
Flaking / Scaling	Not present	Isolated scale, specific to lesion	Scale <50%	Scale >50%	Scaling extending outside treatment area
Crusting	Not present	Isolated crusting	Crusting <50%	Crusting >50%	Crusting extending outside treatment area
Swelling	Not present	Slight, lesion specific edema	Palpable edema extending beyond individual lesions	Confluent and/or visible edema	Marked swelling extending outside treatment area
Vesiculation / Pustulation	Not present	Vesicles only	Transudate or pustules, with or without vesicles <50%	Transudate or pustules, with or without vesicles >50%	Transudate or pustules, with or without vesicles extending outside treatment area
Erosion / Ulceration	Not present	Lesion specific erosion	Erosion extending beyond individual lesions	Erosion >50%	Black eschar or ulceration

Examples of LSR signs are shown in photographs in [Appendix 1](#).¹⁵

Application site reactions not classified as LSRs (eg, pruritus, pain, infection) will be reported as adverse events.

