9.7.1.8.8 OTHER ANALYSES

Local Skin Reactions

Local skin reactions as reported by the Investigator will be displayed and summarized by visit and cohort for all subjects.

Pigmentation and Scarring

Pigmentation and scarring as reported by the Investigator will be displayed and summarized by visit and cohort for all subjects.

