3 INTRODUCTION

This Statistical Analysis Plan (SAP) is based on the protocol for study KX01-AK-002 Amendment 2, v3.0, dated 26SEP2016. This SAP supersedes the statistical section of the protocol and provides data analysis details for the activity and safety data analysis in the clinical study report (CSR). It does not include information regarding the pharmacokinetic (PK) analysis of the study drug, KX2-391 Ointment 1.0%; that information is provided separately.

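### SAP 5.5.2 lets a local skin reaction grade taken after the first application serve as baseline, contrary to the protocol's pre-application Day 1 baseline

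*SAP*

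**What the plan says.** **SAP.** Section 5.5.2 defines the reference value for LSRs: "LSR baseline grades are defined as the LSR grades recorded at Day 1 (either pre-dose or post-dose". The section uses that baseline in two kinds of output: shift tables for each sign (to the worst later grade and to Day 57), and change from baseline in a composite score that sums the six sign grades.

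**Protocol.** The Day 1 LSR entry in the schedule carries footnote d in Table 1 (Cohort 1) and footnote e in Table 2 (Cohort 2). Both read: "Assessment performed before study medication application. Day 1 evaluation will serve as baseline for these assessments". Section 9.5.1.5.8 separately fixes the time of grading: "Before study medication application (on dosing days". Grading begins only after Screening: "At every post-Screening clinic visit through Day 57 (Visit 10), the Investigator or trained designee will assess any LSR". The protocol's planned analysis in 9.7.1.8.8 was by visit only: "Local skin reactions as reported by the Investigator will be displayed and summarized by visit and cohort for all subjects". The change, shift and composite outputs were added by the SAP.

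**The concern.** A baseline should describe the skin before exposure. A grade taken after the first application may already contain the reaction that the table is meant to measure. The window need not be short: under protocol 9.1, subjects may stay at the site for about 5 hours on Day 1 for pharmacokinetic sampling.

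LSRs are named in the SAP's safety endpoint (5.1.2), and contrasting the two regimens on safety is a secondary objective (SAP 3.1.2). If post-application grades were more common in one cohort than in the other, the descriptive contrast between regimens would be affected as well.

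**Working it through.** The plan states no figure on this point, so there is none to reproduce. The check is a comparison of the text, followed by arithmetic on assumed grades.

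**1. Does anything in the SAP resolve the conflict?**

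- *Precedence (SAP section 3):* "This SAP supersedes the statistical section of the protocol". The pre-application baseline is not in that section of the protocol. It is in the schedule footnotes and the assessment section. Protocol 9.7 sets no LSR baseline.
- *Changes in the planned analyses (SAP section 7):* lists other changes, but not this one.
- *General baseline rule (SAP 8.1):* takes the last value before or on first dosing, but gives way where another section says something different. Section 5.5.2 does.

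The conflict therefore stands.

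**2. What happens to one sign in one subject?** The grades below are assumed. *Pre* and *post* are Day 1 grades before and after application. Under the protocol baseline, the post-application grade counts as post-baseline.

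| Assumed grades | Protocol baseline: to worst; to Day 57 | Post-application baseline: to worst; to Day 57 |
|---|---|---|
| pre 0, post 0, later worst 3, Day 57 0 | 0 to 3; 0 to 0 | 0 to 3; 0 to 0 |
| pre 0, post 1, later worst 3, Day 57 0 | 0 to 3; 0 to 0 | 1 to 3; 1 to 0 |
| pre 0, post 1, later worst 1, Day 57 0 | 0 to 1; 0 to 0 | 1 to 1; 1 to 0 |
| pre 0, post 2, later worst 1, Day 57 0 | 0 to 2; 0 to 0 | 2 to 1; 2 to 0 |
| pre 1, post 0, later worst 3, Day 57 0 | 1 to 3; 1 to 0 | 0 to 3; 0 to 0 |

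- Row 1: with no change before grading, there is no error.
- Rows 2 and 3: a one-grade rise shrinks or removes the shift to worst and creates an improvement at Day 57 that did not occur.
- Row 4: the error in shift to worst is 2 − (−1) = 3 grades, more than the Day 1 rise of 2.
- Row 5: if application masks a sign, the error runs the other way. A pre-application grade of 1 is possible, because grade 1 flaking/scaling in protocol Table 6 is "Isolated scale, specific to lesion".

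Each affected subject is counted in the wrong cell. With 80 planned per cohort, that is 1/80 = 1.25 percentage points.

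**3. What happens to the mean composite change?** If the composite rose by k points before grading, the change at each later visit is too low by k. If a share f of the cohort has such a baseline, with mean rise k, the error in the cohort mean is −f × k. The documents give neither f nor k. Over an assumed range:

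| f | k = 1 | k = 2 | k = 3 |
|---|---|---|---|
| 5% | −0.05 | −0.10 | −0.15 |
| 10% | −0.10 | −0.20 | −0.30 |
| 25% | −0.25 | −0.50 | −0.75 |
| 50% | −0.50 | −1.00 | −1.50 |

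The composite runs from 0 to 6 × 4 = 24. The error is zero if f or k is zero.

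**4. Which outputs do not move?** By-visit grades after Day 1, the listed grades and the primary endpoint do not use this baseline. Worst post-baseline incidence moves only if a post-application Day 1 grade exceeds every later grade. The Day 1 row of the by-visit table may mix grades taken before and after application.

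**The case against.** The strongest reply is that the reach is narrow and perhaps nil. The protocol schedules one Day 1 LSR assessment, before application, so a post-application grade would be a deviation. The outputs concerned are descriptive, in an uncontrolled study. Day 2 grading precedes the second application, so a reaction still present then is counted as post-baseline anyway. Where only a post-application grade exists, no definition recovers the missing value. All of this stands, and it limits the weight of the point. It does not justify naming a post-dose grade as an acceptable baseline without declaring or explaining the change.

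Four stronger readings are tempting, and the documents do not support them.

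- *The missing rule for subjects with both grades is a defect of equal weight.* Two Day 1 grades could arise only from an unscheduled record, and it is arguable that SAP 8.1 would settle the tie.
- *The SAP contradicts its own adverse event rule.* Section 5.5.1 classifies the onset of events. A baseline is a reference value on a graded scale, and the protocol reports LSRs separately from adverse events.
- *The SAP treats pigmentation and scarring more strictly.* Section 5.5.3 sets no baseline, so 8.1 applies, and 8.1 can also admit a same-day record that has no time.
- *The wording proves that such records exist.* The SAP was written with study data in view (5.2.6.1 describes doses received), so this is a fair inference, but it is not proof.

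**Conclusion.** The point holds. SAP 5.5.2 departs from the protocol's LSR baseline without declaring it, and it gives wrong shift and composite-change values for any subject whose grade had changed before a post-application Day 1 assessment. An early rise understates the reaction; a masked sign overstates it.

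The size is unknown and may be zero. The 1.25 percentage points per subject rests on the planned 80 per cohort. The grades in the examples and the 0.05 to 1.5 point range for the mean composite error are assumptions, not estimates. A reader might infer that LSR severity is materially understated, or that the regimen contrast is biased in a known direction. The documents support neither, because they do not show how many subjects are affected, in which cohort, or which way their grades moved.

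This should be corrected. It does not bear on the primary conclusion.

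**What to change.** 1. Define LSR baseline in SAP 5.5.2 as the last Day 1 grade before the first application, and treat any post-application Day 1 grade as post-baseline. This also settles the unscheduled case of two grades.
2. Report by cohort, and flag in the listings, the subjects known to have only a post-application Day 1 grade.
3. Present the LSR shift and composite-change tables both with these subjects (their post-application grade standing in as baseline, and labelled so) and without them. Which version is the main one is open to debate, because SAP 5.5 assigns safety output to all dosed subjects. The comparison is what matters.
4. Record the rule in SAP section 7. If timing is unknown for some Day 1 grades, say so and state how they are classified. Footnote the Day 1 row if it mixes timings.
5. If there are no such subjects, delete the words that admit a post-dose grade.

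**Cost.** A few sentences, one count per cohort and a second version of the affected tables. Two limits remain. The true shift of these subjects cannot be recovered, because no LSR grade is taken at Screening. The count may also be incomplete: the protocol says "The time when the study medication application is completed (Application Completion Time) will be recorded", but does not say that the time of the LSR assessment is recorded.
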